10.3.2 Concomitant therapies

Concomitant medications and significant non-drug therapies prior to and after the start of the study drug treatment will be listed by patient and summarized by ATC term by means of contingency tables. The FAS will be used.

10.3.3 Compliance

Compliance to the protocol will be assessed by the number and proportion of patients with protocol deviations. These will be identified prior to database lock and will be listed and summarized.

10.4 Primary objective

The primary objective of this study is to estimate the overall activity of INC280 in advanced HCC patients with c-MET dysregulation. Please refer to [Table 3-1](#) for the primary objective.

10.4.1 Variable

TTP, as per local assessment, is defined as the time from the date of baseline evaluation to the date of the first documented radiological confirmation of disease progression or death due to underlying cancer (RECIST v1.1). If a patient has not had the event at the date of analysis cut-off or when he/she received any further anti-neoplastic therapy, TTP will be censored at the time of the last adequate assessment before the cut-off date.

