7.1.2 Screening

The clinical screening period starts once a patient has provided written informed consent to participate in the study and ends on the day of study entry. Screening assessments have to be done within 14 days prior to the first dose of INC280. Patients' demographics and other characteristics data to be collected include: general demography, relevant medical history/current medical conditions, diagnosis of HCC, extent of cancer (using BCLC staging classification-[Appendix 3](#)) for study eligibility evaluation, and prior antineoplastic therapies (medication, radiation and surgery), CPC ([Appendix 2](#)), physical examination, height and weight, vital signs, ECOG performance status, cardiac assessment, safety laboratory assessments including hematology, biochemistry, coagulation and pregnancy tests. Other assessments will include the special laboratory assessments such as hepatitis markers. Clinical and radiological tumor assessment by RECIST ([Appendix 1](#)) should be conducted preferably within 1 week (7 days) prior to the first dose of the study drug; however tumor assessments up to 3 weeks (21 days) prior to the first dose will be acceptable. During screening, the disease must be staged. The tumor assessment made during the screening phase will provide the baseline tumor measurements, which will be used to determine future responses and/or progression. A complete list of screening evaluations is provided in the visit of assessments table ([Table 7-1](#)).

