7.2 Assessment types

7.2.1 Efficacy assessments

Evidence of clinical efficacy will be evaluated based on radiographic tumor assessments. Tumor response will be evaluated using RECIST version 1.1. (See [Appendix 1](#) for complete details) including the additional modifications described later in this section.

Tumor assessments are required for screening purposes to determine baseline disease at study entry. Both measurable and non-measurable lesions must be assessed and target lesions identified at the baseline visit. Scans performed within 21 days of treatment start can be used as the baseline assessments.

Schedule of tumor assessments

The scheduled tumor assessments are as follows:

- At screening (preferably 7 days prior to 1st dose, however, scans within 21 days of 1st dose are acceptable).
- Day 1 (\pm 7 days) of every other cycle starting from C2D1, (i.e C2D1, C4D1, C6D1, etc).
- At the EOT if a scan was not conducted within 30 days prior to EOT.

Tumor assessments at baseline/screening

The following tumor assessments are to be performed at baseline/screening:

- Chest, abdomen and pelvis CT or MRI scan, including dual-phase imaging of the entire liver
- Brain CT or MRI scan (only if clinically indicated to exclude CNS metastases)
- If bone metastases are suspected, a whole body bone scan (e.g., Tc99m bone scan, NaF positron emission tomography (PET) or whole body bone MRI). Any skeletal lesions identified on the bone scan at baseline that are not visible on the chest, abdomen and pelvis CT or MRI scan, should be imaged with localized CT, MRI or x-ray at baseline.
- Color photography if skin lesions are present (it is recommended to include a ruler to estimate the size of the lesion).

Tumor assessments after baseline/screening

The following tumor assessments are to be performed after baseline/screening:

- Chest, abdomen (including dual-phase imaging of the entire liver), pelvis CT or MRI scan
- Any skeletal lesions identified at baseline that are not visible on the chest and/or abdomen and/or pelvis CT or MRI scan, should be imaged with localized CT, MRI or x-ray at subsequent visits. Whole body bone scans need not be repeated after baseline unless clinically indicated

- Color photography if skin lesions were identified at baseline (it is recommended to include a ruler to estimate the size of the lesion).

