14.1.1 Introduction

The purpose of this document is to provide the working definitions and rules necessary for a consistent and efficient analysis of efficacy for oncology studies in solid tumors. This document is based on the RECIST criteria for tumor responses ([Therasse et al 2000](#)) and the revised RECIST 1.1 guidelines ([Eisenhauer et al 2009](#)).

The efficacy assessments described in [Section 14.1.2](#) and the definition of best response in [Section 14.1.13](#) are based on the RECIST 1.1 criteria but also give more detailed instructions and rules for determination of best response. [Section 14.1.14](#) is summarizing the “time to event” variables and rules which are mainly derived from internal discussions and regulatory consultations, as the RECIST criteria do not define these variables in detail. [Section 14.1.24](#) of this guideline describes data handling and programming rules. This section is to be referred to in the analysis plan(s) to provide further details needed for programming.

As for a usual Novartis template, comments are written in italic font. The protocol authors must take these comments into consideration and provide project or study specific details in the protocol. Specifically, definitions highlighted in red must be discussed, defined and then documented in the study protocol. Any deviations to the guideline must be clearly specified in the protocol with justification.

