14.1.17 Time to progression

TTP is the time from date of randomization/start of treatment to the date of event defined as the first documented progression or death due to underlying cancer. If a patient has not had an event, TTP is censored at the date of last adequate tumor assessment.

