14.1.21 Definition of start and end dates for time to event variables

Assessment date

For each assessment (i.e. evaluation number), the **assessment date** is calculated as the latest of all measurement dates (e.g. X-ray, CT-scan) if the overall lesion response at that assessment is

CR/PR/SD/UNK. Otherwise - if overall lesion response is progression - the assessment date is calculated as the earliest date of all measurement dates at that evaluation number.

Start dates

State in the protocol if date of randomization or date of start of treatment is to be used for all definitions. For randomized studies specify exactly where the randomization date comes from, e.g. from IVRS, or if start of treatment is used as randomization date. For non-randomized studies please specify which treatment start date is taken if more than one treatment is to be given.

For all “time to event” variables, other than the duration of responses, the randomization/ date of treatment start will be used as the start date.

For the calculation of duration of responses the following start date should be used:

- Date of first documented response is the assessment date of the first overall lesion response of CR (for duration of overall complete response) or CR / PR (for duration of overall response) respectively, when this status is later confirmed.

End dates

The end dates which are used to calculate ‘time to event’ variables are defined as follows:

- Date of death (during treatment as recorded on the treatment completion page or during follow-up as recorded on the study evaluation completion page or the survival follow-up page).
- Date of progression is the first assessment date at which the overall lesion response was recorded as PD.

When there is no documentation of radiologic evidence of progression, and the patient discontinued for ‘Disease progression’ due to documented clinical deterioration of disease, the date of discontinuation is used as date of progression.

- Date of last adequate tumor assessment is the date the last tumor assessment with overall lesion response of CR, PR or SD which was made before an event or a censoring reason occurred. In this case the last tumor evaluation date at that assessment is used. If no post-baseline assessments are available (before an event or a censoring reason occurred) the date of randomization/start of treatment is used.

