14.1.30 Calculation of 'time to event' variables

Time to event = end date - start date + 1 (in days)

When no post-baseline tumor assessments are available, the date of randomization/start of treatment will be used as end date (duration = 1 day) when time is to be censored at last tumor assessment, i.e. time to event variables can never be negative.

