2.1.1 General definitions

Study drug and study treatment

Both **study drug** and **study treatment** refer to the study compound: INC280.

Date of first administration of study treatment

The date of first administration of study treatment is derived as the first date when a non-zero dose of study treatment was administered as per the Dosage Administration eCRF.

Date of last administration of study treatment

The date of last administration of study treatment is derived as the last date when a nonzero dose of study treatment was administered as per the Dosage Administration eCRF.

Study day

The study day for safety and efficacy assessments will be calculated as the difference between the date of the event (onset date of an event, assessment date etc.) and the start of study treatment plus 1. The first day of study treatment is therefore study Day 1. Example: if start of study treatment is on 05-Jan-2014 and start date of an adverse event is on 09-Jan-2014 then the study day of the adverse event onset is 5. For safety assessments before start of study treatment, the study day is negative and derived by (date of event - start date of study treatment). For example: if start of study treatment is on 05-Jan-2014 and date of lab measurement is on 02-Jan-2014 then the study day of the laboratory abnormality is -3. Note, the day of start of study treatment is Day 1, and the day before the date of first study treatment is Day - 1, not day 0.

Baseline

Baseline is the result of an investigation describing the “true” state of the patient before start of study treatment administration.

For safety and efficacy evaluations, the last available assessment on or before the date of start of study treatment is taken as “baseline” assessment. In case time of assessment and time of treatment start is captured, the last available assessment before the treatment start date/time is used for baseline.

In rare cases where multiple measurements meet the baseline definition, with no further flag or label that can identify the chronological order, then the following rule should be applied: If values are from central and local laboratories, the value from central assessment should be considered as baseline.

If patients have no value as defined above, the baseline result will be missing.

On-treatment assessment/event observation periods

The overall observation period will be divided into three mutually exclusive segments:

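### Primary TTP is started at an undefined baseline evaluation date, up to 21 days before first dose, against the protocol's own Appendix 1 and without the justification it requires

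*Protocol*

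**What the plan says.** Protocol 10.4.1 and SAP 2.7.1 use the same words: TTP "is defined as the time from the date of baseline evaluation to the date of the first documented radiological confirmation of disease progression" or death from the underlying cancer.

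Neither says which date this is. The nearest text concerns the tumour baseline:

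- Protocol 7.1.2: "The tumor assessment made during the screening phase will provide the baseline tumor measurements". The scan is preferably done within 7 days before first dose and accepted up to 21 days before.
- Protocol 7.2.1: "Scans performed within 21 days of treatment start can be used as the baseline assessments". Table 7-1 places the scan at day -21 to -1.
- SAP 2.1.1: "the last available assessment on or before the date of start of study treatment is taken as" baseline, for safety and efficacy alike.

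Appendix 1 has a different origin. In 14.1.17, "TTP is the time from date of randomization/start of treatment to the date of event defined as the first documented progression". In 14.1.21, for every time-to-event variable except duration of response, "the randomization/ date of treatment start will be used as the start date". The study is not randomized, so only treatment start applies. On departures from the appendix, 14.1.1 states: "Any deviations to the guideline must be clearly specified in the protocol with justification".

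PFS and OS start at first intake of study treatment (Protocol 10.5.1, SAP Table 2-2).

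**The concern.** The primary endpoint's clock differs from the governing appendix. The departure is stated in 10.4.1 but not justified there, in the rest of 10.4, in section 2.2, in the public amendment text, or in the SAP's section on changes to protocol-specified analyses. Study-specific text would normally take precedence over template text, so this is an unexplained and undefined departure rather than two equal rules in conflict.

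Read literally, each TTP includes time before any drug was taken. There is no control arm to cancel that. Protocol 10.8 and SAP section 3 read the result against fixed numbers: an observed median of at least 4 months and a one-sided 90% lower limit of at least 2.2 months.

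There are also two internal mismatches. The same radiological progression gives a TTP longer than PFS by the scan-to-dose gap. And 10.4.3 and SAP 2.7.3 censor a patient with no post-baseline scan at first dose, which suits a clock that starts there. From the scan, that patient is credited with pre-treatment days at risk.

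**Working it through.** **1. Size of the shift.** Let k be the days from baseline scan to first dose: 1 to 21 by Table 7-1, preferably at most 7 by 7.1.2. Each TTP is k days longer than on a first-dose clock. At 30.4375 days per month:

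- k = 7: 7/30.4375 = 0.23 months, 5.7% of 4 months.
- k = 21: 21/30.4375 = 0.69 months, 17% of 4 months and 38% of the 1.8 months between 2.2 and 4.

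**2. When k changes a patient's side of 4 months.** Scans fall on Day 1 of cycles 2, 4, 6 and so on, within 7 days either way (7.2.1). Cycle 6 Day 1 is study day 5 × 21 + 1 = 106. Four months is 121.75 days, or 120 at 30 days per month.

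- Progression found on time at C6D1: 106 + k ≥ 121.75 needs k ≥ 16 (k ≥ 14 at 30 days per month).
- Scan 7 days late: 113 + k ≥ 121.75 needs k ≥ 9 (k ≥ 7 at 30 days per month).

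**3. Patients censored at first dose.** Appendix 14.1.30 uses end − start + 1. From the scan this is k + 1 = 2 to 22 days; 14.1.30 itself states 1 day.

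**4. Reproducing the plan's figures.** Inputs from 10.8 are exponential TTP, 1.5 patients per month, cut-off 6 months after the last patient, loss rate −log(0.70)/12 per month, a Kaplan-Meier median of at least 4 months and a Brookmeyer-Crowley one-sided 90% lower limit above 2.2 months. With continuous detection, no gap and the untransformed limit, the simulated success probabilities are:

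| True median | N=25 simulated (Table 10-2) | N=40 simulated (Table 10-2) |
|---|---|---|
| 2.2 months | 0.010 (0.01) | 0.002 (0.00) |
| 4 months | 0.470 (0.49) | 0.492 (0.50) |

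All 16 cells of Table 10-2 reproduce within 0.02 for success. Table 10-2 is not in question.

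**5. Effect of the origin on the protocol's scan schedule.** Scans at C2D1, C4D1, C6D1 and so on, uniform within ±7 days; progression dated at the scan; censoring at the last scan; exponential TTP from first dose; the same simulated patients under each gap setting; 20,000 runs per cell. Probability of success, N=25 / N=40:

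| Assumed gap | True median 4 months | True median 2.2 months |
|---|---|---|
| None (first-dose clock) | 0.65 / 0.70 | 0.043 / 0.018 |
| Uniform 1–7 days | 0.66 / 0.70 | 0.046 / 0.017 |
| 80% 1–7, 20% 8–21 days | 0.71 / 0.76 | 0.066 / 0.030 |
| Uniform 1–21 days | 0.81 / 0.87 | 0.137 / 0.083 |

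The rise from 0.49 in Table 10-2 to 0.65 with no gap comes from detecting progression only at scans, not from the origin. The origin effect is the change down each column.

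The typical estimated median at a true 4 months, N=25, is 4.83 months with no gap, 4.93 with 1–7 days and 5.13 with 1–21 days.

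**6. Sensitivity.** The log-log limit changes no cell by more than about 0.005. At 30 days per month, uniform 1–21 days gives 0.843 / 0.898 (true 4) and 0.177 / 0.123 (true 2.2). Under the continuous detection of Table 10-2, uniform 1–21 days moves N=25 from 0.470 to 0.604 (true 4) and from 0.010 to 0.028 (true 2.2): the same direction, with smaller increases.

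**The case against.** Protocol and SAP agree word for word, and Appendix 1 is a template with unresolved choices, so what is strictly missing is a justification and a definition. That is right, but it leaves the PFS and censoring mismatches standing.

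The scan reading is likely rather than certain. SAP 2.1.1 says on or before treatment start, so a zero gap is possible under the SAP alone; the 1-day minimum comes from Table 7-1. That ambiguity is itself part of the problem.

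Long gaps may be uncommon. 7.1.2 prefers 7 days, and 4.1 expects treatment within 14 days of starting screening, so gaps of 15 to 21 days would generally need a scan that predates screening. Uniform 1–21 days is therefore a pessimistic case. Uniform 1–14 days gives about 0.71 / 0.77 at a true 4 months (N=25 / N=40). This narrows the likely effect but does not remove it.

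Tumour growth between scan and first dose counts towards progression and could offset the shift. If the exponential clock is started at the scan, success with the scan origin at a true 4 months is about 0.62 / 0.65 (1–7 days) and 0.69 / 0.74 (1–21 days), close to the no-gap figures. But that redefines the true median as 4 months from the scan. On the same simulated data, changing only the analysis clock, the scan origin still gives 0.69 against 0.53 for the dose origin at N=25 with 1–21 day gaps, and little difference with 1–7 days.

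Decision relevance is limited: the objective is estimation, the success rule appears only in the sample-size sections, and enrolment was halted (SAP section 1). That limits the weight of the success probabilities, not the need for a defined clock.

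**Conclusion.** The concern holds. The primary TTP origin is undefined, departs from Appendix 1 without the justification required by 14.1.1 in the public text, and does not match PFS, OS or the first-dose censoring rule. Should be fixed.

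The added time per patient follows from the stated windows: up to 0.23 months at 7 days and 0.69 months at 21 days. The effect on the success rule depends on gaps the documents do not report. It is negligible if the 7-day preference was met; under uniform 1–21 day gaps success rises by 0.16 to 0.17 at a true 4 months (0.65 to 0.81 at N=25, 0.70 to 0.87 at N=40). Pre-dose tumour growth is not modelled in those figures, and they describe the planned design rather than the final sample.

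The documents do not give the time origin of the 2.2- and 2.8-month benchmarks, so inflation is established only relative to a first-dose clock, not against those benchmarks.

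**What to change.** In Protocol 10.4.1 and SAP 2.7.1, start TTP at the date of first dose of INC280, in line with Appendix 1, PFS, OS and the censoring rule. Keep the baseline-scan origin as a sensitivity analysis, and report the scan-to-first-dose gap (median, range, number over 7 days). If the scan origin is kept as primary, define exactly which date it is and add the justification that 14.1.1 asks for.

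The cost is one line in each document and one programming change, with no new data because both dates are already collected. The reported median TTP would be slightly shorter: about 0.1 month (4.93 against 4.83 in the simulation) if scans met the 7-day preference.

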10.4.2 Statistical hypothesis, model, and method of analysis

The primary TTP analysis will include all patients in the FAS (on an Intention-to Treat (ITT) basis) with patients classified according to the treatment group they were assigned to at baseline (Dose-Determining Part or Expansion Part dose).

For patients in the Dose-Determining Part, TTP will be listed along with overall response.

For patients treated at the Expansion Part dose, the distribution of TTP will be estimated using the Kaplan-Meier method. The median TTP and quantiles (along with one-sided 90% confidence intervals) will be presented. The Kaplan-Meier curve will be presented graphically. TTP rate estimates (along with one-sided 90% CI) at 3 months, 6 months, 9 months and 1 year will be presented, as given by the Kaplan-Meier analysis.

10.4.3 Handling of missing values/censoring/discontinuations

If a patient has not experienced a radiological disease progression or death due to underlying cancer, TTP will be censored at the date of the last adequate tumor assessment, defined as the date the last tumor assessment with overall lesion response of CR, PR or SD which was made before a censoring reason occurred, or the date of first dose of INC280 if no post-baseline assessments are available (See RECIST v1.1).

The reason for discontinuation from study will be summarized and listed, along with dates of first and last study drug treatment, duration of exposure to study drug treatment and date of discontinuation for each patient.

Other missing data will simply be noted as missing on appropriate tables/listings. The FAS will be used.

10.4.4 Supportive analyses

Using the PPS, the TTP analysis may be re-run for patients treated with the Expansion Part dose.

10.5 Secondary objectives

Please refer to [Section 3](#) for the secondary objectives.

10.5.1 Efficacy objective(s)

The efficacy objective of this study is to further assess the clinical activity of INC280 in advanced HCC patients with c-MET dysregulation.

The tumor response will be evaluated based on RECIST V1.1., ORR, DCR, PFS and OS in patients with advanced HCC will be assessed. ORR is defined as the proportion of patients with a best overall response (BOR) of complete response (CR) or PR at any time on study per RECIST. DCR is defined as the proportion of patients with a BOR of CR, PR or SD at any time on study per RECIST. PFS is defined as the time from date of first study treatment intake to the date of the first radiologically documented progression or death due to any cause or initiation of new antineoplastic therapy. If a patient has not had an event, PFS is censored at the date of last adequate tumor assessment. OS is defined as the time from date of first study treatment intake to date of death due to any cause. If a patient is not known to have died, survival will be censored at the date of last contact.

Individual lesion measurements and overall response (investigator's assessment) at each assessment will be listed by patient and treatment group. BOR will be summarized for all patients by treatment group and the observed ORR will be summarized in terms of percentage rates with 95% confidence intervals for each treatment group. The Kaplan-Meier estimates of OS and PFS distribution functions will be presented graphically. The resulting median OS and median PFS and quantile estimates will be provided along with 95% confidence intervals. Rate estimates of PFS and OS (along with 95% CI) at 3 months, 6 months, 9 months and 1 year will be presented, as given by the Kaplan-Meier analysis.

For treatments groups with less than 10 patients, Kaplan-Meier estimates and plots will not be presented.

